6.0 Registration Procedures**6.1 Site Procedures**

6.11 Study staff will need to complete the required training prior to gaining access to the registration application. This is located on the ACCRU web page at [REDACTED] Refer to Study Resources → Applications. Near the bottom of the page there will be a link to the “Research Registration Application Training.” After training is complete, study staff must complete the “Attestation of Training” and send to the ACCRU Registration Office at [REDACTED]

6.12 Documentation of IRB approval must be on file in the Registration Office before an investigator may register any patients. Approvals should be uploaded using Florence.

In addition to submitting initial IRB approval documents, ongoing IRB approval documentation must be on file (no less than annually) with ACCRU. Approvals should be uploaded using Florence. If the necessary documentation is not submitted in advance of attempting patient registration, the randomization will not be accepted and the patient may not be enrolled in the protocol until the situation is resolved.

Submission of annual IRB approvals is required until the study has been closed through your IRB.

6.2 Registration Procedures

6.21 To register a patient, access the ACCRU web page at [REDACTED] go to the Study Resources → Application section and click on “Registration” and enter the registration application. The registration application is available 24 hours a day, 7 days a week. Back up and/or system support contact information is available on the Web site. If unable to access the Web site, call the Academic and Community Cancer Research United (ACCRU) Registration Office at [REDACTED] between the hours of 8 a.m. and 4:30 p.m. Central Time (Monday through Friday).

Instructions for the registration application are available on the above web page under the Study Resources section → Application section. Please refer to the “Research Registration Application Training” or Quick Reference Guide for instructions.

Prior to initiation of protocol study intervention, this process must be completed in its entirety and an ACCRU subject ID number must be available as noted in the instructions. It is the responsibility of the individual and institution registering the patient to confirm the process has been successfully completed prior to release of the study agent. Patient registration via the registration application can be confirmed in any of the following ways:

- Contact the ACCRU Registration Office at [REDACTED] If the patient was fully registered, the Registration Office staff can access the information from the centralized database and confirm the registration.
- Refer to the Research Registration Application training on the ACCRU website under Study Resources → Applications.

□

6.22 Prior to accepting the registration, the registration application will verify the following:

- IRB approval at the registering institution
- Patient eligibility
- Existence of a signed consent form
- Existence of a signed authorization for use and disclosure of protected health information

6.23 Correlative Research

Mandatory

A mandatory correlative research component is part of this study. The patient will be automatically registered onto this component (see Sections 3.0, 14.0 and 17.0).

Optional

An optional correlative research component is part of this study, there will be an option to select if the patient is to be registered onto this component (see Section 17.0).

- Patient has/has not given permission to give his/her tissue sample for research testing.

6.24 At the time of registration, the following will be recorded:

- Patient has/has not given permission to store and use his/her sample(s) for future research to learn about, prevent, or treat cancer.
- Patient has/has not given permission to store and use his/her sample(s) for future research to learn, prevent, or treat other health problems (for example: diabetes, Alzheimer's disease, or heart disease).
- Patient has/has not given permission for ACCRU to give his/her sample(s) to outside researchers.

6.25 Treatment cannot begin prior to registration and must begin ≤ 7 days after registration.

6.26 Pretreatment tests/procedures (see Section 4.0) must be completed within the guidelines specified on the test schedule.

6.27 All required baseline symptoms (see Section 10.5) must be documented and graded.

6.28 Treatment on this protocol must commence at an ACCRU institution under the supervision of a medical oncologist.

7.0 Protocol Treatment

7.1 Treatment Schedule - Use actual weight or estimated dry weight if fluid retention

Agent	Dose	Route	Frequency	ReRx
Olaparib	300mg (Starting dose)	PO	Twice Daily (28 day cycle)	Every 28 days

The planned dose of 300 mg taken twice a day will be made up of two (2) x 150 mg tablets, with 100 mg tablets used to manage dose reductions. The planned dose should be taken at the same times in the morning and evening of each day, approximately 12 hours apart with approximately 240 mL of water. The olaparib tablets should be swallowed whole and not chewed, crushed, dissolved or divided. Olaparib tablets can be taken with or without food.

If vomiting occurs shortly after the olaparib tablets are swallowed, the dose should only be replaced if all of the intact tablets can be seen and counted. Should any patient enrolled on the study miss a scheduled dose for whatever reason (e.g. as a result of forgetting to take the tablets or vomiting), the patient will be allowed to take the scheduled dose up to a maximum of 2 hours after that scheduled dose time. If greater than 2 hours after the scheduled dose time, the missed dose is not to be taken and the patient should take their allotted dose at the next scheduled time.

7.2 Patients can be instructed in administration techniques and granted treatment independence with nursing staff approval.

7.3 For this protocol, the patient must return to the consenting ACCRU institution for evaluation at least every 28 days +/- 7 days during treatment.

8.0 Dosage Modification Based on Adverse Events

Any toxicity observed during the course of the study could be managed by interruption of the dose of study treatment or dose reductions. Repeat dose interruptions are allowed as required, for a maximum of 4 weeks on each occasion. If the interruption is any longer, the study team must be informed. Study treatment can be dose reduced to 250 mg twice daily as a first step and to 200 mg twice daily as a second step. If the reduced dose of 200 mg twice daily is not tolerable, no further dose reduction is allowed and study treatment should be discontinued.

Once dose is reduced, escalation is not permitted.

ALERT: ADR reporting may be required for some adverse events (See Section 10)

8.1 Dose Levels

Dose Level	Drug Name	Drug Name
1*	Olaparib	300mg taken orally twice daily
-1	Olaparib	250mg taken orally twice daily
-2	Olaparib	200mg taken orally twice daily

* Dose level 1 refers to the starting dose.

8.2 Dose Modifications

Management of hematological toxicity**Management of anemia**

Hemoglobin	Action to be taken
Hgb < 10 but ≥ 8 g/dl (CTCAE Grade 2)	First occurrence: Give appropriate supportive treatment and investigate causality. Investigator judgement to continue olaparib with supportive treatment (eg transfusion) or interrupt dose for a maximum of 4 weeks. Study treatment can be restarted if Hb has recovered to > 9g/dl. Subsequent occurrences: If Hb < 10 but ≥ 9 g/dl investigator judgement to continue olaparib with supportive treatment (eg transfusion) or dose interrupt (for max of 4 weeks) and upon recovery dose reduction may be considered (to 250 mg twice daily as a first step and to 200 mg twice daily as a second step). If Hb < 9 but ≥ 8 g/dl, dose interrupt (for max of 4weeks) until Hb ≥ 9 g/dl and upon recovery dose reduction may be considered (to 250 mg twice daily as a first step and to 200 mg twice daily as a second step).
Hgb < 8 g/dl (CTCAE Grade 3/4)	Give appropriate supportive treatment (e.g. transfusion) and investigate causality. Interrupt olaparib for a maximum of 4 weeks until improved to Hgb ≥ 10 g/dl. Upon recovery dose reduce to 250 mg twice daily as a first step and to 200 mg twice daily as a second step in the case of repeat Hgb decrease.

Common treatable causes of anemia (e.g., iron, vitamin B12 or folate deficiencies and hypothyroidism) should be investigated and appropriately managed. In some cases management of anemia may require blood transfusions. For cases where patients develop prolonged hematological toxicity (≥2 week interruption/delay in study treatment due to CTCAE grade 3 or worse anemia and/or development of blood transfusion dependence), refer to dedicated section “Management of prolonged hematological toxicities while on study treatment” for the management of these cases.

Management of neutropenia, leukopenia and thrombocytopenia

Toxicity	Study treatment dose adjustment
CTCAE gr 1-2	Investigator judgement to continue treatment or if dose interruption, this should be for a maximum of 4 weeks; appropriate supportive treatment and causality investigation.

CTCAE gr 3-4	Dose interruption until recovered to CTCAE gr 1 for a maximum of 4 weeks, and dose reduction to 250 mg twice daily as a first step and 200 mg twice daily as a second step.
--------------	---

Adverse event of neutropenia and leukopenia should be managed as deemed appropriate by the investigator with close follow up and interruption of study drug if CTCAE grade 3 or worse neutropenia occurs.

Primary prophylaxis with Granulocyte colony-stimulating factor (G-CSF) is not recommended, however, if a patient develops febrile neutropenia, study treatment should be stopped and appropriate management including G-CSF should be given according to local hospital guidelines. Please note that G-CSF should not be used within at least 24 h (7 days for PEGylated G-CSF) of the last dose of study treatment unless absolutely necessary. Platelet transfusions, if indicated, should be done according to local hospital guidelines. Study treatment can be interrupted for CTCAE grade 1 /2 neutropenia or thrombocytopenia as per investigator's judgement. In case of CTCAE grade 3/4 neutropenia, leukopenia or thrombocytopenia, study treatment should be interrupted for a maximum of 4 weeks. Study treatment can be restarted at the same dose if an adverse event of neutropenia, leukopenia or thrombocytopenia has been recovered up to CTCAE grade 1 or less. Any subsequent interruptions will require study treatment dose reductions to 250 mg twice daily as a first step and to 200 mg twice daily as a second step.

Management of prolonged hematological toxicities while on study treatment.

If a patient develops prolonged hematological toxicity such as:

- ≥ 2 week interruption/delay in study treatment due to CTCAE grade 3 or worse anemia and/or development of blood transfusion dependence
- ≥ 2 week interruption/delay in study treatment due to CTCAE grade 3 or worse neutropenia (ANC $< 1 \times 10^9/L$)
- ≥ 2 week interruption/delay in study treatment due to CTCAE grade 3 or worse thrombocytopenia (Platelets $< 50 \times 10^9/L$)

Weekly differential blood counts including reticulocytes and peripheral blood smear should be performed. Study treatment should be discontinued if blood counts do not recover to CTCAE grade 1 or better within 4 weeks of dose interruption. Olaparib treatment should be discontinued if patient's diagnosis of MDS and/or AML is confirmed.

If any blood parameters remain clinically abnormal after 4 weeks of dose interruption, the patient should be referred to hematologist for further investigations. Bone marrow analysis and/or blood cytogenetic analysis should be considered at this stage according to standard hematological practice. Development of a confirmed myelodysplastic syndrome or other clonal blood disorder should be reported as an SAE and full reports must be provided by the investigator to AstraZeneca Patient Safety.

Management of non-hematological toxicity

Repeat dose interruptions are allowed as required, for a maximum of 4 weeks on each occasion. If the interruption is any longer than this the study monitor must be informed. Where toxicity reoccurs following re-challenge with study treatment, and where further dose interruptions are considered inadequate for management of toxicity, then the patient should be considered for dose reduction or must

permanently discontinue study treatment.

Study treatment can be dose reduced to 250 mg twice daily as a first step and to 200 mg twice daily as a second step. Treatment must be interrupted if any NCI-CTCAE grade 3 or 4 adverse event occurs which the investigator considers to be related to administration of study treatment.

Management of nausea and vomiting

Events of nausea and vomiting are known to be associated with olaparib treatment. In study D0810C00019 nausea was reported in 71% of the olaparib treated patients and 36% in the placebo treated patients and vomiting was reported in 34% of the olaparib treated patients and 14% in the placebo treated patients. They are generally mild to moderate (CTCAE grade 1 or 2) severity, intermittent and manageable on continued treatment. The first onset generally occurs in the first month of treatment with the incidence of nausea and vomiting not showing an increase over the treatment cycles.

No routine prophylactic anti-emetic treatment is required at the start of study treatment; however, patients should receive appropriate anti-emetic treatment at the first onset of nausea or vomiting and as required thereafter, in accordance with local treatment practice guidelines. As per international guidance on antiemetic use in cancer patients (ESMO, NCCN), generally a single agent antiemetic should be considered e.g. dopamine receptor antagonist, antihistamines, dexamethasone.

Interruptions for intercurrent non-toxicity related events

Study treatment dose interruption for conditions other than toxicity resolution should be kept as short as possible. If a patient cannot restart study treatment within 4 weeks for resolution of intercurrent conditions not related to disease progression or toxicity, the case should be discussed with Principal Investigator.

All dose reductions and interruptions (including any missed doses), and the reasons for the reductions/interruptions are to be recorded in the eCRF. Study treatment should be stopped at least 3 days prior to planned surgery. After surgery study treatment can be restarted when the wound has healed. No stoppage of study treatment is required for any biopsy procedure.

Study treatment should be discontinued for a minimum of 3 days before a patient undergoes radiation treatment. Study treatment should be restarted within 4 weeks as long as any bone marrow toxicity has recovered.

Repeat dose interruptions are allowed as required, for a maximum of 4 weeks on each occasion. If the interruption is any longer than this the study monitor must be informed. Where toxicity reoccurs following re-challenge with study treatment, and where further dose interruptions are considered inadequate for management of toxicity, then the patient should be considered for dose reduction or must permanently discontinue study treatment.

Study treatment can be dose reduced to 250 mg twice daily as a first step and to 200 mg twice daily as a second step. Treatment must be interrupted if any NCI-CTCAE grade 3 or 4 adverse event occurs which the investigator considers to be related to administration of study treatment. Excludes alopecia, non-refractory nausea/vomiting, non-refractory hypersensitivity and nonclinical and asymptomatic laboratory abnormalities.

Study treatment should be stopped at least 3 days prior to planned surgery. After surgery study treatment

can be restarted when the wound has healed. No stoppage of study treatment is required for any needle biopsy procedure.

Study treatment should be discontinued for a minimum of 3 days before a patient undergoes radiation treatment. Study treatment should be restarted within 4 weeks as long as any bone marrow toxicity has recovered.

Because the adverse effects related to olaparib may include asthenia, fatigue and dizziness, patients should be advised to use caution while driving or using machinery if these symptoms occur.

Management of new or worsening pulmonary symptoms

If new or worsening pulmonary symptoms (e.g. dyspnea) or radiological abnormality occurs, an interruption in study treatment dosing is recommended and a diagnostic workup (including a high resolution CT scan) should be performed, to exclude pneumonitis. Following investigation, if no evidence of abnormality is observed on CT imaging and symptoms resolve, then study treatment can be restarted, if deemed appropriate by the investigator. If significant pulmonary abnormalities are identified, these need to be discussed with the Principal Investigator.

Renal impairment

If subsequent to study entry and while still on study therapy, a patient's estimated CrCl falls below the threshold for study inclusion (≥ 51 ml/min), retesting should be performed promptly.

A dose reduction is recommended for patients who develop moderate renal impairment (calculated creatinine clearance by Cockcroft-Gault equation or based on a 24 hour urine test of between 31 and 50 ml/min) for any reason during the course of the study: the dose of olaparib should be reduced to 200 mg twice daily.

Because the CrCl determination is only an estimate of renal function, in instances where the CrCl falls to between 31 and 50 mL/min, the investigator should use his or her discretion in determining whether a dose change or discontinuation of therapy is warranted.

Olaparib has not been studied in patients with severe renal impairment (creatinine clearance ≤ 30 ml/min) or end-stage renal disease; if patients develop severe impairment or end stage disease it is recommended that olaparib be discontinued.

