
Strong CYP3A inhibitors: itraconazole, telithromycin, clarithromycin, boosted protease inhibitors, indinavir, saquinavir, nelfinavir, boceprevir, telaprevir
 
Moderate CYP3A inhibitors: ciprofloxacin, erythromycin, diltiazem, fluconazole, verapamil
	
Strong or moderate CYP3A inhibitors should not be taken with olaparib. If there is no suitable alternative concomitant medication then the dose of olaparib should be reduced for the period of concomitant administration. The dose reduction of olaparib should be recorded in the CRF with the reason documented as concomitant CYP3A inhibitor use.
 
 Strong CYP3A inhibitors – reduce the dose of olaparib to 100 mg twice daily for the duration of concomitant therapy with the strong inhibitor and for 5 half-lives afterwards. Moderate CYP3A inhibitors - reduce the dose of olaparib to 150 mg twice daily for the duration of concomitant therapy with the moderate inhibitor and for 3 half-lives afterwards. After the washout of the inhibitor is complete, the olaparib dose can be re-escalated.

Strong inducers: phenobarbital, phenytoin, rifampicin, rifabutin, rifapentine, carbamazepine, nevirapine, enzalutamide and St John's Wort
 
Moderate CYP3A inducers: bosentan, efavirenz and modafinil
	
Strong or moderate CYP3A inducers should not be taken with olaparib. If the use of any strong or moderate CYP3A inducers are considered necessary for the patient's safety and welfare this could diminish the clinical efficacy of olaparib.
 
If a patient requires use of a strong or moderate CYP3A inducer then they must be monitored carefully for any change in efficacy of olaparib

Restricted concomitant medications

Medication/class of drug:	Usage (including limits for duration permitted and special situations in which it's allowed):

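### Section 8.2 gives two different restart instructions after a first grade 3–4 neutropenia, leukopenia or thrombocytopenia

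*Combined protocol and SAP*

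**What the plan says.** Section 8.2 of the protocol handles neutropenia, leukopenia and thrombocytopenia twice, first in a two-row table and then in a paragraph.

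- **Table, grade 3–4 row:** "Dose interruption until recovered to CTCAE gr 1 for a maximum of 4 weeks, and dose reduction to 250 mg twice daily", with 200 mg twice daily as the second step.
- **Paragraph, interruption:** "In case of CTCAE grade 3/4 neutropenia, leukopenia or thrombocytopenia, study treatment should be interrupted for a maximum of 4 weeks".
- **Paragraph, restart:** "Study treatment can be restarted at the same dose if an adverse event of neutropenia, leukopenia or thrombocytopenia has been recovered" to grade 1 or better.
- **Paragraph, later events:** "Any subsequent interruptions will require study treatment dose reductions to 250 mg twice daily as a first step", again with 200 mg as the second step.

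Two other passages bear on going back up in dose. Section 8.0, on modifications for adverse events, states: "Once dose is reduced, escalation is not permitted". Section 9.5, on restricted concomitant medications, lowers olaparib to 100 or 150 mg twice daily while a strong or moderate CYP3A inhibitor is given, and then states: "After the washout of the inhibitor is complete, the olaparib dose can be re-escalated".

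**The concern.** The table and the paragraph address the same toxicities at the same grades, with the same recovery threshold and the same four-week limit, but they give different restart doses after a first event. Sites that work from the table and sites that work from the text would treat like patients differently, and each could point to the protocol.

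The stakes are patient safety and consistent dosing. Because Section 8.0 does not allow a reduced dose to be raised again, a reduction made under the table is permanent, and treatment may run for up to 36 cycles (Section 13.4). An event in the first two 28-day cycles would also alter the dose given before the first scan at about 8 weeks, on which the primary endpoint rests (Section 16.21).

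**Working it through.** No figure in the plan depends on this point, so the check is a side-by-side reading followed by a walk down the dose levels.

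**Step 1. Do the two passages cover the same case?** Yes. Both name neutropenia, leukopenia and thrombocytopenia, both name grades 3 and 4, both cap the interruption at four weeks, and both require recovery to grade 1.

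**Step 2. Can the table be confined to repeat events?** Its wording does not do so. The anemia table, in the same section, separates first from subsequent occurrences in its grade 2 row. The grade 3–4 row here has no such label.

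**Step 3. Can the same-dose sentence be confined to grades 1–2?** Nothing in it does so. It comes directly after the sentence on interruption for grade 3/4 events. The sentence after it makes 250 mg the first step at a *later* interruption, which presupposes that a patient on the starting dose was not reduced at the first.

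**Step 4. What doses follow?** Assume a patient starting at 300 mg twice daily (Section 8.1), with no other reductions, whose every grade 3–4 event recovers to grade 1 within four weeks. For the text column, assume the site uses the permission to resume unchanged.

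| Grade 3–4 event | Restart dose, table | Restart dose, text | Difference |
|---|---|---|---|
| First | 250 mg | 300 mg | 50/300 = 16.7% |
| Second | 200 mg | 250 mg | 50/250 = 20% |
| Third | no step left in Section 8.1 | 200 mg | – |

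All doses are twice daily, and each percentage is of the larger dose. Both passages require a reduction at the second event, but from different levels, so the divergence does not close. The steps run out one event sooner under the table.

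**Step 5. How often would this arise?** The documents do not say. Section 15.17 lists neutropenia, leukopenia and decreased platelet count among toxicities seen in more than 10%, but without grade. Section 3.17 admits platelet counts from 75,000/mm³ (75 × 10⁹/L), and Section 8.2 puts grade 3 thrombocytopenia below 50 × 10⁹/L, a gap of 25 × 10⁹/L for a patient at the limit. That makes the case plausible but gives no rate.

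**Step 6. Sections 8.0 and 9.5.** The bar on escalation is unqualified in wording but sits under a heading about adverse events. The permission in 9.5 concerns a temporary reduction with its own end point. They can be read together as a general rule and a specific exception. Three things stay unstated:

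- Neither passage refers to the other.
- The 100 and 150 mg doses do not appear among the dose levels in Section 8.1.
- Nothing says which dose a patient returns to if toxicity had already led to a reduction before the inhibitor was given.

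**The case against.** The strongest defence is that the paragraph only permits an unchanged restart, while the table directs a reduction. A site that always reduces breaches neither passage. That is correct, and it disposes of one tempting inference, that every site must violate something. Only an unchanged restart collides with the table. It does not reconcile the passages, because on that reading the permission could never be used and the sentence tying reduction to later interruptions would have no purpose.

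A reader might also infer more than the documents support:

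- **That re-escalation is flatly both barred and allowed.** Step 6 shows a compatible reading. The heading of Section 8.0 does not settle the matter alone, since Section 8.2 also covers non-toxicity interruptions and a renal dose reduction whatever its cause. What remains is a gap in wording.
- **That the 100 and 150 mg doses break a 200 mg floor.** Section 8.0 rules out further reduction when 200 mg is not tolerated. It does not address drug interactions.
- **That the conflict is certain to occur.** There is no grade 3–4 rate to support this.
- **That patients would become major violations or drop out of the primary analysis.** Section 13.2 requires a cycle 1 departure severe enough to put evaluability in question, and a one-step difference in restart dose under protocol text is unlikely to qualify. Section 16.21 counts any eligible, consented patient who received any treatment, so restart dose removes nobody from the denominator.

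**Conclusion.** The conflict in Section 8.2 is real and is wrong as written: the table and the text give incompatible instructions for the restart dose after a first grade 3–4 neutropenia, leukopenia or thrombocytopenia, and no rule of precedence is given. For a patient on the starting dose the size is 50 mg twice daily (16.7%) at the first event and 50 mg twice daily (20%) at the second, with the reduction steps exhausted one event earlier under the table. This rests on recovery within four weeks, no other reductions, and a text-following site that uses the permission. The frequency is unknown, and any effect on the 8-week endpoint cannot be quantified from the documents. Sample size, power and decision rules are untouched.

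The relation between Sections 8.0 and 9.5 is a secondary point of wording to be clarified. It is not a second contradiction of the same standing.

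**What to change.** 1. Reconcile the grade 3–4 row of the Section 8.2 table with the paragraph below it, so that a single instruction governs the first event. State explicitly what applies to a first and to a later event, even if the answer is the same. Which instruction stands is for the sponsor's clinical team. This review takes no position.
2. In the same amendment, state whether the bar on escalation in Section 8.0 applies to a reduction made only for a CYP3A inhibitor, and what re-escalation in Section 9.5 means for a patient already reduced for toxicity.
3. Send sites a short memo with the reconciled wording.

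The cost is amendment text and the memo. There is no change to sample size, analysis or data collection, since Section 8.2 already requires reductions, interruptions and their reasons to be recorded in the eCRF.

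### Section 8.2 states the interruption rule for related grade 3-4 events twice, and the two statements conflict for four listed categories of event

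*Combined protocol and SAP*

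**What the plan says.** Section 8.2 (Dose Modifications) contains the rule twice.

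- **Under the heading on managing non-hematological toxicity:** "Treatment must be interrupted if any NCI-CTCAE grade 3 or 4 adverse event occurs", provided that the investigator judges the event to be drug-related. Nothing else qualifies the sentence. The next line is the heading for nausea and vomiting.
- **Under the heading "Interruptions for intercurrent non-toxicity related events":** the same sentence is repeated word for word. Directly after it comes "Excludes alopecia, non-refractory nausea/vomiting, non-refractory hypersensitivity and nonclinical and asymptomatic laboratory abnormalities".

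Two other places might have been expected to settle the matter. Section 8.0 opens with "Any toxicity observed during the course of the study could be managed by interruption of the dose of study treatment or dose reductions", which is permissive and does not mention the grade 3-4 rule. The nausea and vomiting text in Section 8.2 says of those events "They are generally mild to moderate (CTCAE grade 1 or 2) severity, intermittent and manageable on continued treatment" and then gives anti-emetic advice. It does not say what happens to dosing at grade 3 or 4.

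**The concern.** An instruction worded with *must* should have one version. Here it has two, and the one with exceptions sits under a heading for interruptions that are not due to toxicity. An investigator looking up how to handle a toxicity has little reason to read that far.

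Consistency of dosing and classification of deviations are at stake. Section 8.2 requires interruptions and their reasons to be recorded in the eCRF, and Section 18.1 provides a deviation form. Whether continued dosing through, say, a related grade 3 asymptomatic laboratory abnormality is a deviation depends on which paragraph the site or monitor applies.

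**Working it through.** The plan gives no figure on this point, so the check is a comparison of texts.

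**Step 1: what each statement requires.** The exclusion is a fragment with no subject. It is read here as qualifying the sentence just before it, which is the natural reading of its position.

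| Related grade 3-4 event | Non-hematological toxicity text | Repeated text, with exclusions | Agree? |
|---|---|---|---|
| Alopecia | Interrupt | Interruption not required | No |
| Nausea/vomiting, non-refractory | Interrupt | Interruption not required | No |
| Hypersensitivity, non-refractory | Interrupt | Interruption not required | No |
| Laboratory abnormality, nonclinical and asymptomatic | Interrupt | Interruption not required | No |
| Nausea/vomiting or hypersensitivity, refractory | Interrupt | Interrupt | Yes |
| Any other non-hematological event | Interrupt | Interrupt | Yes |

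**Step 2: what a site can do in the four conflicting rows.** The repeated text lifts the duty to interrupt; it does not forbid interruption.

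- A site that interrupts complies with both statements.
- A site that continues dosing complies with the repeated text and deviates from the other.

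The conflict is therefore mandatory against not mandatory.

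**Step 3: does anything resolve it?** Sections 8.0, 8.2, 9.0 and 13.0 contain no cross-reference, order of precedence or statement of which text governs.

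**Step 4: does it look deliberate?** The surrounding text suggests two versions that were not merged. The surgery and radiotherapy instructions also appear twice under the same heading. The surgery repeat differs in one word: no stoppage is needed for any biopsy in one place, and for any needle biopsy in the other. This is an inference from the layout, since the documents do not explain it.

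**Step 5: what else in the plan depends on the rule?**

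- *Primary endpoint (Section 16.21):* success is being alive without progression at the first scan, among eligible, consenting patients who took any study treatment. Neither the scoring nor the evaluable set refers to interruptions.
- *Error rates (Section 16.22):* these follow from the stage sizes, the cut-offs and the assumed success proportions of 0.5 and 0.7. None of these changes.
- *Adverse event stopping rule (Section 16.52):* it counts clinically relevant, at least possibly related grade 3 or higher non-hematologic events, whether or not dosing was interrupted.

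**The case against.** The best defence is that both statements are in Section 8.2 and the second is the first with a qualifier attached. Someone reading the whole section could take them together as a general rule and its exceptions. That reading is available, but the text does not state it, and the heading over the exclusions points away from it. The defence shows that sites would not necessarily diverge; it does not remove the contradiction.

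A reader might infer more than the documents support, in four ways.

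- *That the two texts demand opposite actions.* They do not, because interrupting satisfies both.
- *That the problem is common.* The nausea and vomiting text cites 71% and 34% in olaparib-treated patients of an earlier study. Those figures are not restricted by grade, and the same text calls the events generally grade 1 or 2. The conflict needs a grade 3-4 event that is related and, for nausea and vomiting, non-refractory. No rate for that is given.
- *That half the time to the primary endpoint is at risk.* Dividing the 4-week maximum interruption by the roughly 8 weeks to the first scan gives 4/8 = one half. That is a ceiling for any single interruption under any rule. It does not measure the difference between the two readings.
- *That the primary result could be altered through evaluability.* Section 13.2 does allow a severe breach of cycle 1 treatment requirements to put evaluability in question. But the evaluable set in Section 16.21 does not exclude such patients, and nothing says that continued dosing through a listed event would count as severe. An indirect effect through drug exposure is possible, but the documents offer no way to quantify it.

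**Conclusion.** The inconsistency is real and confined to the four listed categories. For those, the same section makes interruption both mandatory and not mandatory, so continued dosing is compliant under one text and a deviation under the other. For all other related grade 3-4 non-hematological events the texts agree.

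Its frequency cannot be sized from the documents. Its consequences lie in dosing consistency and deviation classification; the endpoint definition, the error rates and the stopping rule stand as they are. The conclusion rests on one reading, that the exclusion list qualifies the sentence immediately before it.

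This is an internal inconsistency arising from duplicated text, not a design choice. It should be corrected because it concerns a safety instruction and is cheap to correct. Which of the two rules is clinically right is outside this point.

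**What to change.** Reconcile the two passages in this order.

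1. The clinical team decides whether the exclusion list applies and, if so, to which events. That includes saying whether its laboratory category is meant to touch the blood count abnormalities that have their own rules earlier in Section 8.2. The repeat is not under the non-hematological heading, so its reach is unclear.
2. State the rule once, under the toxicity heading, with or without the list as decided.
3. Delete the repeat from the text on non-toxicity interruptions. The repeat holds the only copy of the list, so deleting it before step 1 would settle a clinical question by accident; leaving it in place would do the same in the other direction.
4. In the same edit, reconcile the duplicated surgery, biopsy and radiotherapy instructions.

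The cost is one clinical decision and a short text change in an amendment. No change to the design, sample size or analysis is needed.
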